#### CONFIDENTIAL

interventions. *In the current study, we will build upon this past work to conduct a pilot study to test the feasibility of an intervention designed to prevent homelessness among ED patients with unhealthy alcohol or drug use.*

## **2.2 Rationale**

The goal of this study is to test the feasibility and acceptability of implementing a homelessness prevention intervention for ED patients with unhealthy alcohol or drug use who are at risk for homelessness. It is important to conduct this pilot feasibility study because there have been no prior studies of ED-based homelessness prevention interventions, and therefore a pilot study is an appropriate first step in expanding our knowledge and determining whether and how future interventions and studies will be possible. Given that this is a feasibility study, the choice of a single-arm study (intervention arm only) is appropriate. This feasibility study will inform a larger future trial of homelessness prevention interventions for substance using ED patients. Attempting to prevent homelessness among ED patients is important for the reasons stated in section 2.1.

## **2.3 Potential Risks & Benefits**

### **2.3.1 Known Potential Risks**

There is no known risk from the intervention itself. The study presents minimal risks. Study subjects are not expected to face any physical or financial risks as a result of participating in the study. Legal risks to study subjects are minimal despite the sensitive nature of some study questions, given that all study subject information will be treated as confidential and securely protected, and a NIH Certificate of Confidentiality has been obtained for this study. There are small risks of psychological discomfort, fear that refusal to participate will affect health care services, and potential breach of confidentiality.

1. Discomfort associated with answering personal questions during study surveys/assessments (immediate risk): Participants will complete surveys that include questions on health status, mental health, substance abuse, socioeconomic status, homelessness and housing, and other topics that may cause personal discomfort or anxiety. In the informed consent process, participants will be instructed that they can divulge as little or as much as they choose and are free to withdraw from the study at any time and for any reason.

2. Fear that refusal to participate will affect care or services (immediate risk): Given that participants will be recruited while they are patients in the Bellevue Hospital ED, they may fear that refusal to participate in the study will adversely affect the care they receive. This risk is minimal because research staff who will be enrolling patients into the study are not part of the patients' treatment teams, and it will be clearly explained to potential participants that refusal to participate will in no way affect their care in the Bellevue Hospital ED.

3. Potential breaches of confidentiality (immediate and long-term risk): There is a small risk of breach of confidentiality. A breach of confidentiality could potentially be damaging to study subjects if personally identifying information was released along with their answers to the baseline surveys. Such a breach is improbable, however, because of the safeguards that will be taken around the storage of personally identifying information.

Given the steps that we will take to minimize the chances of breach of confidentiality and other risks, participating in this study presents low risk and thus the risk/benefit ratio is favorable, particularly given the potential benefits to participants described below. Further, the knowledge gained from the proposed research has the potential to benefit future ED patients who are at risk for homelessness.

### **2.3.2 Known Potential Benefits**

All participants in the study will receive an intervention that includes: 1) Referral to Homebase homelessness prevention services offered by community-based organizations in NYC; 2) Referral to substance use services (SBIRT and Addiction Leads / peer counselor) available at Bellevue Hospital; 3)

CONFIDENTIAL

Follow-up to ensure patients receive needed services. A prior randomized controlled trial showed that people receiving Homebase services in NYC had lower risk of entering a homeless shelter in the future. Therefore, one potential benefit to pilot study participants is that they will be referred to—and if they go and are found eligible will receive—services that may reduce their risk for future homelessness. Participants will also receive referrals to appropriate substance use services that are already offered at the study hospital, including SBIRT (screening, brief intervention, and referral to treatment) and peer navigator/social work services (Addiction Leads). Prior research has suggested that receipt of such services in the ED may improve substance use related outcomes for some patients, particularly those with unhealthy alcohol use.

### **3 Objectives and Purpose**

The primary objective of this study is to test the feasibility and acceptability of implementing a homelessness prevention intervention for ED patients with unhealthy alcohol or drug use who are at risk for homelessness. Accomplishing this objective will allow us to modify the intervention and study designs to be proposed for a future larger, multisite study that will include testing for outcomes/efficacy.

#### **3.1 Primary Objective**

The primary objective of this study is to test the feasibility and acceptability of implementing a homelessness prevention intervention for ED patients with unhealthy alcohol or drug use who are at risk for homelessness.

#### **3.2 Secondary Objectives (if applicable)**

Not applicable.

### **4 Study Design and Endpoints**

#### **4.1 Description of Study Design**

We will conduct a single-arm (intervention only) pilot feasibility study of a homelessness prevention and substance use intervention for Bellevue Hospital ED patients with unhealthy alcohol or drug use who are at risk for future homelessness, with longitudinal follow-up to 6 months after the baseline visit.

#### **4.2 Study Endpoints**

##### **4.2.1 Primary Study Endpoints**

Given the primary study objective around feasibility and acceptability, the primary study endpoints represent a constellation of feasibility and acceptability measures that will be informative in modifying/developing a future larger intervention study. We will track the number of patients approached, the number screening positive for unhealthy alcohol or drug use, the number screening positive for homelessness risk, and the number of those eligible for the intervention who agree to participate. We will track reasons for study ineligibility and refusal, and will compare basic characteristics (e.g., gender, age, race, drug and alcohol use) of those who agreed and did not agree to participate. We will also track the number and location of referrals made for homelessness prevention and/or substance use services, the number of appointments kept, the number and types of homelessness prevention and other services actually received, and the length of time between the ED intervention and receipt of services. We will track the ability to contact patients for the 6-month follow-up interview (e.g., number of calls needed). Data sources for these feasibility endpoints include the *ED-Home Baseline Screening and Survey* (see attachment) and the participant tracking and follow-up information that will be documented on REDCap (*ED-Home Follow-up Procedures Form* and *ED-Home Tracking Form*) and using a tracking log in Excel that will be used internally to manage participant status, attempts of contact with participants, attempts of contact with providers, and necessary follow-up steps; no protected health information will be recorded on the Excel tracking log. In addition, we will gather information on acceptability of and satisfaction with both the overall intervention and its individual components from patients both immediately after the intervention is provided (while they are in the ED) and at the 6-month follow-up interview using a series of intervention assessment questions contained in the

CONFIDENTIAL

baseline and follow-up surveys (see [ED-Home Baseline Screening and Survey](#) and [ED-Home 6-Month Follow-up Survey](#)). At the 6 month follow-up interview, as part of the [ED-Home 6-Month Follow-up Survey](#), we will use the [Housing Risk Flyer](#) as well as a NYC HRA YouTube video. We will also speak with stakeholders (e.g., ED providers, homelessness prevention service providers) to obtain feedback on the intervention and factors to enhance its future implementation and sustainability.

#### **4.2.2 Secondary Study Endpoints**

Not applicable.

#### **4.2.3 Exploratory Endpoints**

Exploratory outcomes will include new onset homelessness as measured by entry into a homeless shelter within 6 months of the ED intervention (determined using the Department of Social Services CARES database), multiple self-reported housing status and substance use measures at the 6-month follow-up interview (see [ED-Home 6 Month Follow-Up Survey](#) and [Additional Baseline and Follow-up Questionnaires](#) attachments), and measures of health services use (see [ED-Home EMR Data Abstraction Tool](#)). Although we are not powering the study to show statistically significant effects on these outcomes, we will be able to determine feasibility of outcome measurement and gain a preliminary sense of potential intervention effects.

### **5 Study Enrollment and Withdrawal**

#### **5.1 Inclusion Criteria**

In order to be eligible to participate in this study, an individual must meet all of the following criteria:

1. Be a patient in the Bellevue Hospital Center ED (including the Adult Emergency Services, Pediatric Emergency Services if  $\geq 18$  years old, and Urgent Care).
2. Be  $\geq 18$  years old.
3. Screen positive for homelessness risk using the homelessness risk screening tool (HRST).
4. Screen positive for unhealthy alcohol or drug use.
5. Able and willing to provide consent.

All participants must be able to and agree to provide informed consent to study participation.

#### **5.2 Exclusion Criteria**

An individual who meets any of the following criteria will be excluded from participation in this study:

1. Medically (e.g., critically ill) or psychiatrically unstable.
2. Unable to provide informed consent for other reason (e.g., dementia or other cognitive deficit, profound intoxication).
3. Incarcerated or in police custody.
4. Unable to understand and speak English.
5. Lives outside NYC and/or cannot give a NYC ZIP code.
6. Already homeless (residing in a shelter or on the streets).
7. Does not have a telephone where can be reached for follow-up.
8. Has already received specialized peer navigator/addiction social worker services (Addiction LEADs) during current ED visit.
9. Has already participated in the study.

Non-English speaking patients are being excluded because English-speakers are at highest risk for shelter entry in New York City, and our primary patients of interest for this intervention are those at risk for shelter entry. Limited resources for this small pilot feasibility study preclude us from providing the translation and staffing necessary to enroll lower risk language groups.

#### **5.3 Vulnerable Subjects**

Children under the age of 18 will be excluded from the study. Pregnant women will not be excluded because pregnancy is a known risk factor for future homelessness. This research does not pose any risk to the fetus.

CONFIDENTIAL

This material is the property of the NYU School of Medicine and Langone Health Medical Center. Do not disclose or use except as authorized in writing by the study sponsor

Patients who are not currently incarcerated, under arrest, or otherwise detained but who may be on probation or parole will not be excluded from the study as these patients are not considered prisoners for research and may be at particularly high risk for future homelessness and could benefit from homelessness prevention interventions. It is expected that most participants found to be eligible for the study will be from socioeconomically disadvantaged groups, as the study is targeted to patients who are at risk for future homelessness. Further information on potential risks and benefits appears in section 2.3.

#### **5.4 Strategies for Recruitment and Retention**

Study participants will be recruited exclusively in the Bellevue Hospital ED (including AES, PES, and UC). ED patients will be approached by trained study RAs to screen for study eligibility (see ED-Home Baseline Procedures flow chart in Schematic of Study Design section). Patients will only be approached during periods when they are not receiving active clinical care (e.g., RAs will not interrupt if a doctor or nurse is talking with the patient). Patients who are medically or psychiatrically unstable will also not be approached.

We will use a random sampling scheme of adult ED patients. Trained Research Assistants (RAs) will begin each shift in a randomly assigned section of the ED to start patient recruitment for the shift (these sections include the “sides” of the AES, the UC, and the PES). The RA will then approach patients sequentially beginning with a random first patient in the randomly assigned patient area and moving systematically through sequential areas of the ED once covering the initial area. RAs may use the publically displayed “white boards” located in all sections of the ED to assist in identifying appropriate patients for screening; for example, the “white boards” display patient age and location, which will assist RAs in identifying patients who are ≥18 years old. In addition to the random sampling scheme as described above, it is possible that ED care providers may identify specific patients who they feel would benefit from the study and may ask RAs to screen those patients for eligibility. In those cases, the RA/RC can break the random sampling scheme but will make a note in REDCap that this was done so that we can track recruitment processes for our feasibility study outcomes.

Study procedures including screening and informed consent will occur in the Bellevue Hospital ED. Multiple steps will be taken to maximize patient privacy, including: asking any visitors to leave the room/area; moving patients to private or semi-private areas of the ED when feasible; speaking in a low voice near patients’ heads.

Upon approaching patients, RAs will explain that they are conducting a research study and obtain patient verbal assent to complete screening questions for study eligibility. A standard screening tool will be used, with RAs guided through the screening and entering question responses in real-time using REDCap (see ED-Home Baseline Screening and Survey attachment). Patients who are found eligible for the study will be invited to participate. The informed consent process will be conducted by the study RC and will include explaining to patients what will occur in the study, what information they will be asked to give, and who receives and can use this information (see ED-Home Informed Consent and ED-Home Key Information Sheet attachment). Written informed consent is required for study participation. Participants will sign two consent forms; one copy to retain themselves and the other for study records. For participants in whom capacity to complete informed consent is questionable, a validated consent capacity quiz will be completed (see ED-Home UBACC attachment) and/or research staff will discuss with the patient’s treating provider prior to obtaining written informed consent.

Participant retention will be enhanced in the following ways:

- Detailed locator information will be collected from each participant. This information will include multiple contact phone numbers and other information that will enhance our ability to contact participants for follow-up procedures. See ED-Home Locator Form attachment for full details.
- Participants will be given a study contact card and sticker to allow them to contact study staff proactively as needed, for example, if their contact information has changed. See ED-Home Study Contact Card and Sticker attachment.
- Follow-up participant contact including follow-up visit reminders will occur in the manner and schedule outlined in the ED-Home Baseline Procedures flow chart in the Schematic of Study Design section.

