## **10 Statistical Considerations**

### **10.1 Statistical and Analytical Plans**

There will not be a formal SAP for this small feasibility pilot study.

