#### **10.4.2 Analysis of the Primary Efficacy Endpoint(s)**

There are not primary efficacy endpoints for this study. Rather, the primary endpoints are measures of intervention/study feasibility. The main analyses for feasibility will involve simple descriptive analyses examining endpoints including:

- Number of patients approached, number (percent) screening positive for unhealthy alcohol or drug use, number (percent) screening positive for homelessness risk.
- Number (percent) of those approached who are eligible for the study. Number (percent) reasons for ineligibility.
- Number (percent) of those eligible who agree to participate. Number (percent) reasons for refusal.
- Basic characteristics (e.g., gender, age, race, primary drug vs. alcohol use) of those who were eligible vs. ineligible and agreed and did not agree to participate using descriptive statistics and bivariate analysis.
- Number and location of referrals made for homelessness prevention and/or substance use services. Number and types of homelessness prevention and other services actually received. Length of time between the ED intervention and receipt of services.
- Participant satisfaction and self-efficacy measures as assessed at baseline and 6 month follow-up visits.

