## **12 Quality Assurance and Quality Control**

Multiple steps will be taken toward quality assurance (QA) and quality control (QC).

- All study staff, including RAs and RC, will be thoroughly trained both in overall GCP and human subjects protections and in study-specific procedures.
  - Formal training will occur prior to the study beginning recruitment.
  - Continuous training will occur in weekly staff team meetings.
- RAs will be closely supervised by the RC, with PI oversight. The RC will be supervised by the PI.
- A SOP document will clearly outline all study procedures, including QA/QC procedures.
- Multiple QA/QC protections are built into REDCap data collection software being used for this study, including forced question entry (i.e., specified questions cannot be left blank), automatic logging of all activities in REDCap including any entry changes, and study staff permission rules.

CONFIDENTIAL

- All paper forms, including consent forms, will be regularly reviewed (both at the time of initial completion and at least weekly) for completeness.
- Weekly QA/QC reviews between the PI/RC will include:
  - Review of numbers of patients approached, eligible/ineligible, refused, participated.
  - Review to ensure that all eligibility classifications were made correctly.
  - Review for missing or out of range data.
  - Review of any potential QA/QC issues identified by any study staff member (which did not warrant more immediate discussion).

The PI and RC will oversee QA and QC efforts.

The investigational site will provide direct access to all trial related sites, source data/documents, and reports for the purpose of monitoring and auditing by the sponsor, and inspection by local and regulatory authorities.

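### Do the recruitment counts lose track of patients whom ED providers put forward outside the random scheme?

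*Combined protocol and SAP*

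**What the plan says.** Under section 5.4, research assistants start each shift in a randomly assigned part of the ED, with a random first patient, and then move on sequentially. The same section allows a second route: "ED care providers may identify specific patients who they feel would benefit from the study", and staff may be asked to screen them. When that happens, staff "will make a note in REDCap that this was done so that we can track recruitment processes for our feasibility study outcomes".

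The counts appear in three places:

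- Section 4.2.1, primary endpoints: "We will track the number of patients approached, the number screening positive for unhealthy alcohol or drug use", the number positive for homelessness risk, and "the number of those eligible for the intervention who agree to participate".
- Section 10.4.2, analysis: "Number (percent) of those approached who are eligible for the study" and "Number (percent) of those eligible who agree to participate", with reasons for ineligibility and refusal. The list is introduced as non-exhaustive, and the section adds that associations with feasibility outcomes may be examined.
- Section 12, weekly quality review: "Review of numbers of patients approached, eligible/ineligible, refused, participated".

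None of the three names a count by recruitment route. Section 10.1 states: "There will not be a formal SAP for this small feasibility pilot study". Section 10.2 says that the primary endpoints are descriptive and carry no testable hypotheses. Section 10.5 gives about 40 patients, without a power calculation.

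**The concern.** Providers would put forward patients they expect to benefit. Such patients could well screen positive, be eligible or consent at rates different from those met on the random route. Pooling both routes into one percentage would then mix the yield of systematic approach with the yield of clinical referral. These counts are primary endpoints, and section 3 says that the pilot will shape a larger multisite study. A planner who took the overall eligibility percentage as the yield of systematic approach could underestimate how many patients must be approached. With no separate SAP, section 10 is the natural place for a rule on this, and it has none. Section 5.4 creates the note and the analysis section never mentions it again, which looks like a loose end.

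**Working it through.** **1. The passages side by side.** Three things would have to be true for this to be a defect.

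- *The route is not captured.* It is: section 5.4 requires a note in REDCap.
- *The note has no analytic purpose.* It has one: section 5.4 ties it to the feasibility outcomes, which are the primary endpoints.
- *The analysis excludes a split or prescribes pooling.* It does neither: the list in 10.4.2 is open, and no passage addresses pooling.

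Section 12 carries little weight here. It lists weekly checks on conduct and does not prescribe reporting.

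**2. The one planning figure.** Section 10.5 equates about 40 patients with 1–2 per week over 6 months. Taking 6 months as 26 weeks, 40 / 26 = 1.54 per week, and 1–2 per week gives 26–52 patients. The figure reproduces and does not depend on route.

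**3. A bound without assumptions.** Let w be the provider-identified share of a denominator, and p_nom and p_rand the rates on the two routes. Then

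overall − random-route = w × (p_nom − p_rand).

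The difference of two proportions lies between −1 and 1, so the gap is at most w: 1 point at w = 1%, 5 points at 5%, 10 points at 10%. It is zero if the rates are equal. The documents give neither w nor the rates, so everything below is illustration.

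**4. Consent, assuming 60% overall.** 40 / 0.60 = 66.7, so about 67 eligible. The 95% half-width is 1.96 × √(0.60 × 0.40 / 67) = 0.117, or 11.7 points. For a 20-point difference between routes:

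| Provider-identified among 67 | Shift in overall figure |
|---|---|
| 3 | 3/67 × 20 = 0.9 points |
| 7 | 7/67 × 20 = 2.1 points |
| 12 | 12/67 × 20 = 3.6 points |

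To find when the gap matches the half-width, hold the overall result at 40 of 67.

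- If all provider-identified patients consent, 15 of them give 40/67 − 25/52 = 11.6 points, and 16 give 40/67 − 24/51 = 12.6 points.
- If none consents, 11 of them give 40/67 − 40/56 = −11.7 points.

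So it takes about 11 to 16 of the 67, at the extremes of consent behaviour.

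**5. Eligibility, assuming 5% on the random route.** With 67 eligible, the relative 95% half-width is about 1.96 / √67 = 0.239. With a share f of approaches provider-identified, overall / random-route = 1 + f × (R − 1), where R = p_nom / p_rand. The ratio passes 1.239 when R exceeds 1 + 0.239 / f.

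| f | R needed | p_nom needed |
|---|---|---|
| 1% | 24.9 | 125%, impossible |
| 5% | 5.8 | 29% |
| 10% | 3.4 | 17% |

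At f = 1%, even if every such patient is eligible, the ratio is only 0.99 + 0.01 × 20 = 1.19.

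**6. A wider range for eligibility.** Assume 5–10% eligible on the random route, 30–50% among provider-identified patients, and 2–20% of approaches provider-identified.

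- Low end: 0.98 × 0.10 + 0.02 × 0.30 = 0.104 overall. Provider-identified patients are 0.006 / 0.104 = 6% of those eligible.
- High end: 0.80 × 0.05 + 0.20 × 0.50 = 0.14 overall. Provider-identified patients are 0.10 / 0.14 = 71% of those eligible.

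**The case for a change.** The strongest case is that an open list permits a split without promising one. How patients were found is itself a feasibility result, as section 5.4 acknowledges. The high end of step 6 shows that, if providers referred often and well, an overall eligibility of 14% could sit beside a random-route rate of 5%. Only counts by route would reveal that, and one sentence in 10.4.2 would guarantee them.

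Part of this stands. No count by route is named in the three sections, and a table by route could be informative. But it shows a detail left to reporting, not a wrong analysis. The percentage of all those approached who are eligible is exactly what 10.4.2 asks for, so the overall figure is a correct answer to the endpoint as defined. If referrals turn out to be common, the REDCap note lets the split be made without new data or a change to any endpoint. Section 5.4 itself presents the second route only as a possibility and expects no particular share.

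The random-route column would not be a clean estimate of ED yield either. The scheme is a random start followed by sequential approach, and it passes over unstable patients and those in active care. It is not a probability sample of ED visits, so choosing that column would not turn a biased figure into an unbiased one.

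The flow charts, the screening form and the operating procedures were not available for this check and may already name such a count. The conclusion does not depend on that.

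**Conclusion.** The concern does not hold. The plan records each departure from the random scheme, states that the record serves the feasibility outcomes, and leaves the descriptive list open. Followed as written, it gives sound descriptive results for the endpoints it defines. No test, threshold or sample size changes with the route.

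The only firm statement on size is that the overall and random-route percentages cannot differ by more than the provider-identified share of the denominator. On the assumed consent rate of 60%, a 20-point difference with 3 to 12 such patients among 67 moves the overall figure by 0.9 to 3.6 points, inside a half-width of 11.7 points. Eligibility could move more if referrals were frequent. All rates used are assumptions, because the documents give none. Whether to show the counts by route is a presentation choice still open to the investigators when they report.
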